5.2.1.6 Laboratory Assessments

Clinical laboratory variables for hematology, chemistry including liver function test, coagulation, urinalysis, and bone marrow will be collected during the conduct of the study as listed in [Table 6](#) below.

Additional laboratory tests should be performed according to institutional standard of care.

Table 6 Laboratory Assessments

Clinical Laboratory Tests

Panel/Assessments	Parameters to be Analyzed	NCI-CTCAE Grading (Hyper/Hypo)
CBC with Differential	Hematocrit (Hct) Hemoglobin (Hgb) Platelet count Red blood cell count (RBC) White blood cell count (WBC) White blood cell count differential Absolute neutrophil count Absolute lymphocyte count	NA Both Hypo NA Both NA Hypo Both
Biochemistry	Sodium (Na) Potassium (K) Chloride (Cl) Bicarbonate (HCO3) Blood urea nitrogen (BUN) Creatinine (Cr) Glucose (Gl) Calcium (Ca) Phosphorus Magnesium (Mg) Albumin (Alb) Total protein (T Prot) Alkaline phosphatase (ALP) Lactate dehydrogenase (LDH) Creatine phosphokinase (CPK) Liver function tests including*: Bilirubin total (TBL) Alanine aminotransferase (ALT) Aspartate aminotransferase (AST)	Both Both NA NA NA Hyper Both Both NA Both Hypo NA Hyper NA Hyper Hyper Hyper Hyper
Table continues next page		

Panel/Assessments	Parameters to be Analyzed	NCI-CTCAE Grading (Hyper/Hypo)
Urinalysis	Color Appearance Specific gravity pH Bilirubin Blood Glucose Ketones Leukocyte esterase Nitrite Protein Urobilinogen	NA NA NA NA NA NA NA NA NA NA NA NA
Urine/Serum Pregnancy Test *	hCG (Positive/Negative)	NA
Coagulation Profile (PT/INR, D-Dimer, Fibrinogen)	Activated partial thromboplastin time (aPTT) International normalized ratio (INR) Prothrombin time (sec) (PT) Fibrinogen D-Dimer	Hyper Hyper NA NA NA

eCRF: electronic case report form; hCG: human chorionic gonadotrophin.

* Local results will be collected and entered into the eCRF.

5.2.1.7 Vital Signs

Vital signs will include:

- Systolic and diastolic blood pressures (mmHg)
- Pulse rate (beats/minute)
- Respiratory Rate (breaths/min)
- Body temperature (degrees C)
- Height (m) (Height measurement performed at screening only) and weight (kg)

5.2.1.8 Electrocardiogram (ECG)

12-lead ECGs will be recorded in triplicate at the scheduled time points. Each ECG tracing will be taken 2 minutes apart. ECGs will be read at the site for clinical decision making and transmitted to a central reviewer. Data from the central reviewer will be used in summary presentations.

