- At C1D1 and any visit when pembrolizumab and ASP7517 are administered together, vital signs are obtained predose (-1 h from start of pembrolizumab infusion), within 15 min prior to start of the pembrolizumab infusion, 15 min (-5 to +10 min window) after the start of pembrolizumab infusion, at the end of pembrolizumab infusion (-5 to +10 min window), 30 min (\pm 10 min) after completion of the pembrolizumab infusion, within 15 min prior to start of ASP7517 infusion, every 15 min (-5 to +10 min window) during ASP7517 infusion, at the end of ASP7517 infusion (-5 to +10 min window), and postdose (+30 min, +1, +2, +3 and +4 h [\pm 10 min window each] from end of the ASP7517 infusion).
- ASP7517 dosing only: Vital signs will be obtained within 15 min prior to start of the ASP7517 infusion, every 15 min (-5 to +10 min window) during the ASP7517 infusion, at the end of the ASP7517 infusion (-5 to + 10 min window), as well as 30 min (\pm 5 min), 1 h (\pm 10 min) and 2 h (\pm 10 min) after completion of the ASP7517 infusion. If participants are still available, additional optional vital sign assessments 3 h (\pm 10 min) and 4 h (\pm 10 min) after completion of the ASP7517 infusion will be obtained.
- Pembrolizumab dosing only: Vital signs will be obtained within 15 min prior to start of the pembrolizumab infusion, 15 min (-5 to +10 min window) after the start of the pembrolizumab infusion, at the end of the pembrolizumab infusion (-5 to + 10 min window) and at 30 min (\pm 10 min) after completion of the pembrolizumab infusion for participants in the combination therapy.

f. Obtain predose.

g. If chest X-ray is performed prior to 2 weeks of screening (prior to ICF and performed as part of standard of care), then it does not need to be repeated.

h. During ASP7517 and pembrolizumab combination therapy, 12-lead ECGs will be recorded in triplicate (at least 2 min apart per time point) and transmitted electronically for central reading. After treatment with ASP7517 has been discontinued, 12-lead ECGs will be recorded as a single assessment (in triplicate if deemed necessary, at least 2 min apart per time point) and read locally. ECG may be repeated once during screening. On IP administration days, ECGs will be obtained:

- At C1D1 and any visit when pembrolizumab and ASP7517 are administered together, ECGs are obtained predose (-1 h from start of pembrolizumab infusion) and 1 to 2 h post dose.

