7.2.4 Electrocardiogram

A standard 12-lead ECG will be performed at the screening visit for purposes of assessing participant eligibility. ECG can be repeated during the screening period.

For Dose Escalation:

12-lead ECGs will be recorded in triplicate (at least 2 min apart per time point) and transmitted electronically for central reading. ECGs may be repeated once during screening. On IP administration days, ECGs will be obtained:

- At C1D1 and any visit when pembrolizumab and ASP7517 are administered together, ECGs are obtained predose (-1 h from start of pembrolizumab infusion) and 1 to 2 h post dose of ASP7517.
- ASP7517 dosing only: ECGs are obtained predose (-1 h from start of ASP7517 infusion) and 1 to 2 h post dose of ASP7517.
- Pembrolizumab dosing only: ECGs are obtained predose (-1 h from start of pembrolizumab infusion) and 1 to 2 h post dose of pembrolizumab.

For Dose Expansion:

During ASP7517 and pembrolizumab combination therapy, 12-lead ECGs will be recorded in triplicate (at least 2 min apart per time point) and transmitted electronically for central reading. After treatment with ASP7517 has been discontinued, 12-lead ECGs will be recorded as a single assessment (in triplicate if deemed necessary, at least 2 min apart per

time point) and read locally. On IP administration days, ECG will be obtained predose and 1 to 2 hours post dose. ECG may be repeated once during screening.

ECGs will be recorded after the participant has been in a resting, supine position for at least 5 min. Further details of the procedure will be separately specified in the procedural manual.

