6.5.6 Electrocardiograms (ECGs)

The three values of each ECG parameter within a time point from the central reviewer will be averaged to determine time-specific parameter for a participant, and used in summaries.

ECG variables will be summarized using mean, standard deviation, minimum, maximum and median for each dose level, phase, tumor type, and overall at each treatment visit and time point, including changes from baseline.

Number and percentage of participants with normal and abnormal results as assessed by central review for the overall interpretation will be tabulated by dose level, phase, tumor type, and overall at each treatment visit and time point. A shift analysis table showing shift in overall ECG interpretation from baseline to each time point will be provided. The worst of the three overall ECG interpretations will be used as the time-specific overall ECG interpretation for a participant.

The QT interval corrected for heart rate by Fridericia's formula, QTcF, is defined as: $QTc(F) = QT/(RR)^{0.33}$, where RR interval is inversely proportional to heart rate (approximately RR = 60/heart rate).

The QTcF interval will be summarized using frequency tables for each treatment visit and time point for values of clinical importance using the range criteria below.

	QTc Interval Criteria Value (msec)	
	Cumulative Category	Interval Category
Normal	≤ 450	≤ 450
Borderline	> 450	> 450 to ≤ 480
Prolonged	> 480	> 480 to ≤ 500
Clinically significant	> 500	> 500

The QTcF interval will also be summarized by the frequencies of participants with a change from baseline of clinical importance using the criteria identified below. These summaries will be provided for each treatment visit and time point.

Variable	Change from Baseline	
	Cumulative Category	Interval Category
QTc Interval (msec)	<0	<0
	≥ 0	≥ 0 to ≤ 30
	> 30	> 30 to ≤ 60
	> 60	> 60

Number and percent of participants with 12 lead ECG abnormalities as well as number and percent of participants whose 12 lead ECG reading changed from normal at baseline to abnormal will be tabulated by dose level, phase, tumor type, and overall at each treatment visit and time point.

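### The SAP's rule of tabulating only central triplicate ECGs leaves out the single, locally read phase 2 ECGs taken after ASP7517 stops, mainly during pembrolizumab continuation

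*SAP*

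**What the plan says.** SAP 5.2.1.8 makes no exception by phase or period: "12-lead ECGs will be recorded in triplicate at the scheduled time points". It sends the tracings to a central reviewer and adds: "Data from the central reviewer will be used in summary presentations". SAP 6.5.6 builds its derivation on that: "The three values of each ECG parameter within a time point from the central reviewer will be averaged". For the overall interpretation it takes the worst of the three, and normal or abnormal is as judged centrally. It sets the scope of the continuous summaries as "at each treatment visit and time point, including changes from baseline".

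Protocol 7.2.4 separates the two phases. For dose escalation, "12-lead ECGs will be recorded in triplicate (at least 2 min apart per time point) and transmitted electronically for central reading", and days with pembrolizumab dosing only are included. For dose expansion the same applies during combination therapy, but the mode then changes. Table 2 footnote h says: "After treatment with ASP7517 has been discontinued, 12-lead ECGs will be recorded as a single assessment". Both places allow a triplicate if it is thought necessary, and both have these ECGs read locally.

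Table 4 schedules an ECG at the six-weekly Observation Period visits on pembrolizumab alone and at the 30-, 60- and 90-day safety visits. Protocol 9.4.3.4.1 asks for ECG results and interpretations to be summarised by arm, dose level and time point, without limiting this to central readings, and for values and interpretations to be listed.

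**The concern.** The SAP describes one recording and reading mode for the whole study, while the protocol describes two for phase 2. A programmer following SAP 6.5.6 needs three central values per time point. Once ASP7517 has stopped in dose expansion, there is normally one value and it is local. The SAP has no rule for that case, so the ECG is not tabulated.

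ECGs are part of the primary safety endpoint. The period affected is pembrolizumab alone. Table 17 lists myocarditis among the immune-related events to manage, and Protocol 10.10 notes that such events can arise months after the last pembrolizumab dose. Nothing in a central-only table would tell the reader that the phase 2 continuation visits are absent.

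**Working it through.** The plan gives no figure to reproduce, and the point rests on no power or error-rate calculation. The check compares the rules and counts the visits.

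1. **Which ECGs are single and local.** Under Protocol 7.2.4 and Table 2 footnote h, these are the dose-expansion ECGs after ASP7517 is discontinued. For combination participants who go on to pembrolizumab alone, this covers the Observation Period visits in Table 4. It also covers the end-of-treatment (EOT) visit, which Table 2 footnote s places after the 17th pembrolizumab dose or after the decision to stop.

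2. **What the SAP tables need.** The mean of three central values, or the worst of three central interpretations. A single local reading supplies neither, and SAP 5.2.1.8 and 6.5.6 contain no fallback. Taken literally, none of the ECGs in step 1 enters the tables.

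3. **Whether these visits are in scope.** SAP 6.5.6 refers to treatment visits. Protocol Table 9 lists pembrolizumab as an investigational product, and EOT is deferred until pembrolizumab ends, so pembrolizumab-only dosing visits are reasonably treatment visits. The 30-, 60- and 90-day visits come after EOT, and the wording does not settle whether they count.

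4. **Visits per phase 2 combination participant** who completes six cycles and all pembrolizumab:
   - maximum pembrolizumab doses in the study: 17 (Table 4 footnote e)
   - maximum in the treatment period: 4 (Protocol 4.1.3)
   - continuation visits: 17 - 4 = 13
   - with EOT: 13 + 1 = 14
   - with the three safety visits, if they were meant to be tabulated: 14 + 3 = 17

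   These are visits, not tracings. Protocol 7.2.4 calls for ECGs before and after dosing on treatment days, while Table 4 marks the ECG as predose. If ASP7517 stops early and pembrolizumab continues, the number of pembrolizumab-only visits can exceed 13.

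5. **Dose escalation (phase 1).** Protocol 7.2.4 keeps triplicate recording and central reading, including on pembrolizumab-only days, with no switch after ASP7517 stops. Visits losing central data: 0.

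6. **Phase 2 monotherapy.** The dose-expansion paragraph opens with combination therapy, and the single, local sentence follows as its contrast. The mode for monotherapy participants is not stated. If the sentence applies to them, EOT plus three safety visits (1 + 3 = 4) are single and local. If it does not, the count is 0.

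**The case against.** The strongest case on the other side has four parts.

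- **Consistency.** Restricting quantitative ECG tables to central triplicate means is defensible. Single local readings are less precise and come from different readers, so mixing them into the same table could mislead. This stands, and it argues for a separate panel. It does not justify a SAP that describes all scheduled ECGs as triplicate when the protocol says otherwise.
- **Safety signals are not lost.** Protocol 9.4.3.4.1 commits to listing ECG values and interpretations. Clinically significant ECG abnormalities not due to the underlying disease are reportable as adverse events (Protocol 10.3.1 and 10.3.1.1). Treatment-emergent events are tabulated up to 30 days after the last investigational product, and immune-related events have their own table (SAP 6.5.3). This stands and limits the consequence, though listings do not replace the summaries that the protocol requires.
- **Exclusion is inferred.** The SAP does not say that local readings are discarded. This is true, but its derivation gives them no place.
- **Numbers may be small.** SAP 5.1.1 and the SAP revision history record early closure, so few participants may have reached phase 2 continuation. This stands.

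A reader might infer that every ECG from pembrolizumab continuation and safety follow-up disappears, that the tables cover only the ASP7517 period, and that this applies to the roughly 361 planned phase 2 participants. The documents do not support that. Dose-escalation ECGs keep central readings throughout. The follow-up visits may be outside the tables whoever reads them. The monotherapy mode is unclear, and the planned total is not a realistic denominator after early closure. Nor does the SAP's statement that independent central review data are unavailable bear on ECGs, since it concerns tumour response.

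**Conclusion.** The point holds for phase 2. The SAP contradicts the protocol on how ECGs are recorded and read after ASP7517 stops. Applied as written, it omits the pembrolizumab-continuation ECGs from the summary, QTcF-category and shift tables.

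The size is up to 13 visits plus EOT for a combination participant who completes six cycles and all pembrolizumab doses, and none in dose escalation. This rests on two assumptions: that pembrolizumab-only dosing visits count as treatment visits, and that the SAP's three-central-value rule is applied literally. Where a triplicate was taken because it was judged necessary, it is still read locally, so it does not meet the SAP rule either.

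Three things stay open: whether safety follow-up was meant to be tabulated, how phase 2 monotherapy ECGs are read after ASP7517, and how many participants are affected. Given the listings and adverse event tables, this is a low-severity correction and does not threaten the safety conclusions.

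**What to change.** Correct SAP 5.2.1.8 so that it describes the same recording and reading modes as Protocol 7.2.4, by phase and by whether ASP7517 has stopped, and state which mode applies to phase 2 monotherapy.

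In SAP 6.5.6, keep the central triplicate means and worst-of-three interpretations for the main tables. Add a separate panel, labelled as local readings, for phase 2 visits after ASP7517 stops. It should show observed values, QTcF categories and the shift from normal to abnormal, with a stated rule for the occasional local triplicate. Name the visits in each panel, and say explicitly whether EOT and the 30-, 60- and 90-day visits are tabulated.

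The cost is a few sentences of SAP text, a derivation flag and a little programming, with no protocol change and no new ECGs. The drawback is that local single readings are less precise and cannot be compared directly with central means, including a centrally read baseline. The separate, labelled panel makes that limit visible.

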5.2.1.9 Eastern Cooperative Oncology Group Performance Status (ECOG PS)

The ECOG Scale [Oken et al., 1982] will be used to assess performance status at time points outlined in the Protocol in the Schedule of Assessments.

5.3 Pharmacokinetic Variables

Cellular DNA load of ASP7517 and serum concentrations of Pembrolizumab will be evaluated for each cohort as outlined in the Protocol in the Schedule of Assessments.

5.4 Pharmacodynamic Variables

Pharmacodynamic effects of ASP7517 as monotherapy or in combination with pembrolizumab will be assessed with:

- Cytokine expression and secretion (e.g., IFNg)
- WT1-specific T lymphocytes (e.g., cytotoxic T lymphocytes)
- Immune cell populations (NKT cells, NK cells, etc.)
- Anti-WT1 antibodies
- Tumor microenvironment variables

5.5 Other Variables

- Duration of exposure (days)
 - Duration of exposure to a study drug will be calculated in days, using the following formula:
 - (Last date of exposure – date of first dose) + 1; where last date of exposure= initial infusion date of the last cycle + 27 or death date if death occurs within last cycle.
 - When the start or stop date is missing, then the exposure will be treated as missing.
- Cumulative actual dose (# of cells)
 - Total amount of IP administered to the participant from first dose date to last dose date
- Number of cycles initiated
 - Total number of cycles with non-zero dosing in the cycle
- Planned dose intensity
 - Planned dose/planned number of cycles
- Actual dose intensity
 - Defined as the cumulative actual dose divided by number of cycles
- Relative dose intensity (RDI; %)
 - Actual Dose Intensity
 - x 100
 - Planned Dose Intensity

6 STATISTICAL METHODOLOGY

6.1 General Considerations

For continuous variables, descriptive statistics will include the number of participants (n), mean, standard deviation, median, minimum and maximum. When needed, the use of other percentiles (e.g. 10%, 25%, 75% and 90%) will be reported in the relevant section. In addition, for plasma concentrations and continuous PK parameters, the coefficient of variation and the geometric mean will also be calculated. Frequencies and percentages will be displayed for categorical data. Percentages by categories will be based on the number of participants with no missing data, i.e. will add up to 100%. Kaplan-Meier estimates will be calculated for time-to-event variables and median survival time will be estimated with 2-sided 90% confidence intervals (CI).

Baseline is defined as the last available measurement prior to the first dose of study drug.

Unless otherwise specified, all summaries will be presented overall, by dose level received, and by phase. Separate displays will be presented for monotherapy and combination therapy cohort unless specified otherwise.

All data processing, summarization, and analyses will be performed using SAS® Version 9.4 or higher on Linux. Specifications for table, figure, and data listing formats can be found in the TLF specifications for this study.

Study day will be calculated in reference to the first dose date. For assessments conducted before the first dose, study day will be calculated as (assessment date – first dose date). For assessments conducted on or after the first dose, study day will be calculated as (assessment date – first dose date + 1).

6.2 Study Population

6.2.1 Disposition of Participants

The following participant data will be presented:

- Number and percentage of participants with informed consent, discontinued before allocation to treatment, allocated to treatment (overall only)
- Number and percentage of participants allocated to treatment in each analysis set
- Number and percentage of participants completed and discontinued treatment, by primary reason for treatment discontinuation for SAF
- Number and percentage of participants completed and discontinued the study, by primary reason for study discontinuation for SAF by dose level
- Number and percentage of participants completed and discontinued the study at 30-, 60-, and 90-day follow-up, by primary reason for post-study period discontinuation for SAF
- Number and percentage of participants completed and discontinued the study during the observation period, by primary reason for post-study period discontinuation for SAF

- Number and percentage of participants completed and discontinued the study during the survival follow-up period, by primary reason for post-study period discontinuation for SAF
- For the combination therapy arm, separate summaries for ASP7517 and Pembrolizumab will be provided for End of Treatment disposition.

All disposition details and dates of first and last evaluations for each participant will be listed.

6.2.2 Protocol Deviations

Protocol deviations as defined in the study protocol (Section 8.1.6 Protocol Deviations) will be assessed for all participants enrolled. The number and percentage of participants meeting any criteria will be summarized for each criterion and overall, by dose level, phase, tumor type, and overall as well as by study site. Participants deviating from a criterion more than once will be counted once for the corresponding criterion. Any participants who have more than one protocol deviation will be counted once in the overall summary. A data listing will be provided by site and participant.

The protocol deviation criteria will be uniquely identified in the summary table and listing. The unique identifiers will be as follows:

PD1 - Entered into the study even though they did not satisfy entry criteria,

PD2 - Developed withdrawal criteria during the study and was not withdrawn,

PD3 - Received wrong treatment or incorrect dose,

PD4 - Received excluded concomitant treatment.

PD5 – Informed Consent: Clinical study procedures conducted prior to subject signing informed consent.

PD6 – Safety Reporting: Events not reported within the expected turn-around time per protocol reporting requirements.

PD7 – Procedures and Tests: Missed safety or efficacy assessments related to primary or key secondary endpoints.

6.2.3 Demographic and Other Baseline Characteristics

Demographics and baseline characteristics will be summarized with descriptive statistics.

Number and percentage of participants allocated to treatment in each country and site will be presented by dose level, phase, tumor type, and overall for SAF and FAS.

Descriptive statistics for age, weight, and height at study entry will be presented. Frequency tabulations for sex, ethnicity, age group (≥ 65 years and < 65 years of age), race, region, and baseline ECOG will be presented. This will be done for FAS and RAS.

Medical history and conditions existing at baseline will be coded in MedDRA v26.0 and summarized by System Organ Class (SOC) and Preferred Term (PT) as well as by PT alone, by treatment group and overall for the SAF. Baseline conditions are defined as those ongoing

at the time of informed consent or arise following the time of informed consent and before the first dose of study drug. For ongoing medical conditions, Common Terminology Criteria for Adverse Events (CTCAE) grade will be provided in listing.

